#### 7.3.4.3 Examining Influence of Outliers

Data outliers will be examined through Proc Mixed model residual diagnosis (+/- 4 studentized residuals). The outlier test results will be conducted for the primary endpoint (24-hour total urinary NNAL (ng/24 hours) excreted on Day 7). A sensitivity analysis by excluding outliers will be performed for the primary analysis variable if any outliers are found using the above criteria.

#### 7.3.4.4 Handling BLQ values

Values below the limit of quantitation (BLQ) for nicotine and its metabolites, COHb, and other urine biomarkers will be presented in the data listings as BLQ. Values BLQ for nicotine and metabolites will be set to one-half of the limit of quantitation prior to use in the calculation of nicotine equivalents and data analysis of NE. Values BLQ for other urine biomarkers and COHb will be set to one-half of the LLOQ prior to data analysis. A sensitivity analysis of the primary endpoint (24-hour total urinary NNAL (ng/24 hours) excreted on Day 7) analysis will be conducted by setting the BLQ value to the LLOQ if the percentage of values that are BLQ is greater than 5% of observations.

Approximate LLOQ values for each analyte are shown in the table below. LLOQs will be reported out to the most current validation data and included in the bioanalytical report.

Analyte	LLOQ
Nicotine	50.0 ng/mL
Cotinine	50.0 ng/mL
trans-3'-hydroxycotinine	50.0 ng/mL
nicotine glucuronide	50.0 ng/mL
cotinine glucuronide	200 ng/mL
trans-3'-hydroxycotinine glucuronide	200 ng/mL

NNN	0.500 pg/mL
NNAL	2.00 pg/mL
2-AN	1.7 pg/mL
HEMA	0.2 ng/mL
3-HMPMA	5 ng/mL
3-HPMA	25 ng/mL
CEMA	0.25 ng/mL
4-ABP	1.5 pg/mL
S-PMA	0.02 ng/mL
2-HPMA	2.5 ng/mL
AAMA	10 ng/mL
GAMA	1 ng/mL
2-MHBMA	0.129 ng/mL
2-OHFle	0.05 ng/mL
2-Naphthol	0.10 ng/mL
1-OHP	0.01 ng/mL
Creatinine	30 µg/mL
COHb	0.2%

## 8. SAFETY

No inferential statistics will be performed on the safety data.

All clinical safety data will be listed by subject. Continuous variables will be summarized using n, mean, SD, median, minimum, and maximum. Frequency counts will be reported for all categorical data.

Decimal point will be presented as follows:

- n will be presented without decimal;
- Minimum/maximum in same precision as in the database;
- Mean/median in one more decimal than minimum/maximum;
- SD in one more decimal than mean/median.

Where individual data points are missing because of dropouts or other reasons, the data will be summarized based on reduced denominators.

### 8.1 Subject Disposition

The number of subjects enrolled, the number who completed the study, and the number who did not complete the study (overall and reasons for early withdrawal) will be tabulated by study group and overall. A listing of subjects who discontinued the study prematurely will also be presented. Screen failure subjects and subjects only enrolled in the product trial period will be summarized separately.

## **8.2 Adverse Events**

Adverse events will be coded (to the lowest level term) with the Medical Dictionary for Regulatory Activities (MedDRA®) version 20.0.

A study product use-emergent AE is defined as an AE that is starting or worsening at the time of or after study product administration.

All events captured in the database will be listed in by-subject data listings. However, only study product use-emergent adverse events will be summarized.

Frequencies of subjects with study product use-emergent AEs, regardless of relationship to study product will be summarized by study group and sorted by system organ class. Frequencies of subjects with study product use-emergent serious adverse events will be likewise summarized. Frequencies of study product use-emergent adverse events will be summarized by severity and relationship to study product. Adverse events occurred during the product trial period will be summarized separately as a group.

## **8.3 Clinical Laboratory**

Clinical laboratory evaluations (clinical chemistry, hematology, and urinalysis) will be performed at Screening and at End-of-Study or Early Termination.

Descriptive statistics will be reported for numeric clinical data by study group and time point. Rechecked values prior to randomization will be used in calculating summary statistics. Normal ranges will be listed by site. Subjects only enrolled in the product trial period will be summarized separately.

Out of normal range and clinically significant laboratory values will be listed by subject.

A urine cotinine test will be completed at Screening. Urine drug tests and alcohol breath tests will be completed at Screening. Serum pregnancy tests will be completed at Screening and urine pregnancy tests will be completed at Check-in. Results for these tests will be listed as “Negative” or “Positive.”

## **8.4 Vital Signs**

Vital signs (respiration rate, pulse rate, blood pressure, and oral temperature) will be measured at screening, at Check-in, and at the End-of-Study or upon Early Termination.

Descriptive statistics will be reported for vital sign measurements (blood pressure, pulse, respiration, and temperature) by study group and time point. Post randomization rechecks will not be used for calculation of descriptive statistics. Subjects only enrolled in the product trial period will be summarized separately.

## **8.5 ECG**

A 12-lead ECG will be obtained during screening and listed by subject.

## **8.6 Concomitant Medications**

All concomitant medications recorded during the study will be coded using the WHO Drug Dictionary (WHODD) version 01MAR2018 and listed by subject.

## **8.7 Physical Examination**

Physical examinations will be performed at Screening. A brief physical examination (symptom driven) may be performed at Check-in and End of Study (or Early Termination). Physical examinations will be listed by subject and time point of collection. Changes in physical examinations (if any) will be described in the text of the final report.

# **9. SUMMARY OF CHANGES FROM PROTOCOL-PLANNED ANALYSIS**

The analyses described in this SAP are aligned with those analyses described in the protocol with the following changes for statistical analysis.

1. Mixed model with repeated measurement instead of mixed model will be used in the analysis for biomarker statistical analysis as there are two response values (Days 5 and 7) for each subject.
2. Emax for Use Product Again questionnaire was mentioned in the protocol. As the Use Product Again questionnaire will only be conducted at Day 7 and only one response value for each subject, no maximum value will be available. The analysis will be performed based on the original response.
3. The statistical analysis model for Use Product Again questionnaire was modified based on the study design and data collection.

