#### *Use Product Again Questionnaires*

The maximum response score to the Use the Product Again questionnaire (Emax-upa) for each product will be summarized study product and group. A linear mixed model for analysis of variance will be performed on the Emax scores. The model will include group, study product, and day as fixed effects and subject nested as a random effect. The comparisons of interest will include the VERVE® products compared to subject's OB cigarette. Geometric LSM, 95% confidence intervals, and p-values will be provided for the study products in each response by group.

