6. To compare subjective effects (Questionnaire of Smoking Urges – Brief [QSU-Brief] total score, responses to modified cigarette evaluation questionnaire [mCEQ] and the Use the Product Again questionnaire) among subjects who continue to smoke cigarettes, subjects with dual usage of VERVE® Chews or VERVE® Discs and cigarettes, subjects with complete switch to VERVE® Chews or VERVE® Discs, and subjects who cease from all tobacco use for 1, 5 and 7 days.
7. To characterize product use behaviors (such as: number of cigarettes per day [CPD], number of VERVE® use per day [VPD], average and total duration of VERVE® use each day).

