### **Secondary**

The secondary outcome variables are:

- 24-hour urinary total total NNN, NE, 2-AN, 4-ABP, HEMA, CEMA, S-PMA, 3-HMPMA, 3-HPMA, 2-HPMA, AAMA, GAMA, 2-MHBMA, 2-OHFle, 2-Naphthol, 1-OHPhe, mutagenicity, and 1-OHP excreted on Day 5 and Day 7.
- 24-hour urinary total NNAL excreted on Day 5.
- COHb on Day 5 and Day 7.
- QSU-Brief responses and factor scores on Day 1, Day 5, and Day 7.
- Responses to the appropriate mCEQ on Day 1, Day 5, and Day 7.
- Responses to the appropriate Use the Product Again questionnaire on Day 7.
- Product use behavior daily from Day 1 to Day 7 (i.e., CPD, VPD, and the average and total duration of VERVE® product use each day).

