#### **7.1.4 Subjective Effect**

##### **7.1.4.1 Data Collection**

Subjects will also complete in the moment subjective effects questionnaires, which include:

- QSU-Brief (Protocol Appendix 2) – All subjects will complete the QSU-Brief on Days -1, 1, 5, and 7 in the morning at 07:00 ( $\pm 30$  minutes) before product use, as appropriate, and at 21:30 ( $\pm 30$  minutes).
- Modified Cigarette Evaluation Questionnaire (mCEQ-C or mCEQ-V; Protocol Appendix 3) – the appropriate mCEQ will be administered at 21:30 ( $\pm 30$  minutes). All subjects will complete the mCEQ-C on Day -1. Subjects in Group 1 will also complete the mCEQ-C on Days 1, 5, and 7. Subjects in Groups 2 and 3 will complete both of the mCEQ-C and mCEQ-V on Days 1, 5, and 7. Subjects in Groups 4 and 5 will complete mCEQ-V on Days 1, 5, and 7.
- Use the Product Again questionnaire (Protocol Appendix 4) – Subjects in Groups 1 - 5 will complete the Use the Product Again questionnaire at 21:30 ( $\pm 30$  minutes) on Day 7. Subjects in Group 1 will complete Use the Product Again questionnaire for cigarettes. Subjects in Groups 2 and 3 will complete both Use the Product Again questionnaire for cigarettes and VERVE® products. Subjects

in Groups 4 and 5 will complete Use the Product Again questionnaire for VERVE® products.

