## **7.3.3 Subjective Effects**

Similar statistical comparison analysis (defined in 7.3.1) will be preformed on QSU-brief change from pre-use score and mCEQ original scores (mCEQ-C, among Group 1, 2, and 3; mCEQ-V, among Groups 2, 3, 4, and 5). The comparisons interested for QSU-brief will be the test groups (Groups 2-5) versus the continue smoking group (Group 1) and test groups (Groups 2-5) versus the tobacco cessation Group. The comparisons interested for mCEQ-C will be the dual use groups (Groups 2-3) versus the continue smoking group (Group 1). The comparisons interested for mCEQ-V will be the dual use groups (Groups 2-3) versus the exclusive use group (Groups 4 -5) [i.e. Group 2 vs Group 4 and Group 3 vs Group 5].

This analysis will be conducted on the mITT datasets. No multiple adjustment will be performed for subject effect scores.

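### SAP Section 9 cites a modified Use the Product Again model that the SAP never states, so the planned VERVE versus own-brand cigarette comparison has no contrast, interval or table

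*SAP*

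**What the plan says.** Objective 6, worded alike in the protocol and in SAP 2.3.2, sets out to compare subjective effects across the use patterns and lists "the Use the Product Again questionnaire) among subjects who continue to smoke cigarettes" and the other groups. SAP 2.4 makes it a secondary outcome: "Responses to the appropriate Use the Product Again questionnaire on Day 7".

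Protocol 11.7 gives UPA its own mixed model on the maximum score: "The model will include group, study product, and day as fixed effects and subject nested as a random effect". It also names the contrast: "The comparisons of interest will include the VERVE® products compared to" the subject's own-brand cigarette. Geometric least-squares means, 95% intervals and p-values are promised.

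SAP Section 9 then makes two changes. Item 2 withdraws the maximum score because UPA is given only on Day 7, with "only one response value for each subject". Item 3 says "The statistical analysis model for Use Product Again questionnaire was modified based on the study design and data collection" and stops there.

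On data collection, SAP 7.1.4.1 states: "Subjects in Groups 2 and 3 will complete both Use the Product Again questionnaire for cigarettes and VERVE® products". Group 1 rates cigarettes only, Groups 4 and 5 rate VERVE only, and Group 6 does not complete the form.

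On inference, SAP 7.3.3 opens: "Similar statistical comparison analysis (defined in 7.3.1) will be preformed on QSU-brief change from pre-use score and mCEQ original scores". UPA is not mentioned in that section. SAP 7.2.6 plans frequency counts and descriptive statistics for UPA.

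**The concern.** Item 3 of Section 9 points to a model that cannot be found. A programmer working from the SAP would produce counts and summaries by group and product, and nothing that estimates the contrast the protocol singled out. Anyone who later wanted that contrast would have to choose the model, covariance and comparisons after the data were available. SAP Section 1 treats any analysis not addressed in the SAP as out of scope and needing sponsor approval.

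The dual-use groups are where this matters most. They are the only subjects who rate both products, so they carry the only within-subject VERVE versus cigarette information on this outcome. Summarising each product separately does not give the error of the paired difference.

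**Working it through.** The plan states no sample size, power or effect size for UPA, so there is no figure of its own to reproduce. The check is a trace of UPA through the documents, a count of responses, and a precision figure for scale.

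**1. Inferential output by instrument** (SAP Section 10, list under 14.2.3, counting tables titled as statistical summaries or statistical comparisons)

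- QSU-Brief: 2 (14.2.3.1.2.1, 14.2.3.1.2.2)
- mCEQ: 4 (14.2.3.2.2.1, 14.2.3.2.2.2, 14.2.3.2.3.1, 14.2.3.2.3.2)
- UPA: 0. Tables 14.2.3.3.1 to 14.2.3.3.3 and their shells hold counts and descriptive statistics, with no least-squares mean, difference or p-value.

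**2. Can the protocol's models serve instead?** Not as written.

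- The 11.7 model analyses the maximum score, which SAP Section 9 withdraws.
- It has a day effect, but UPA is collected on one day.
- It reports geometric means, which need positive values. SAP 7.1.4.2 subtracts 50 from the VAS to get a bipolar score running from -50 to 50, so the VAS runs from 0 to 100. The first scale contains negative values and the second can contain zero.
- The general ANCOVA in Protocol 11.9 adjusts for a baseline score, and UPA has none.

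**3. Responses per subject** (planned group sizes from SAP Section 3, forms from SAP 7.1.4.1)

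- Respondents: 40 + 40 + 40 + 30 + 30 = 180
- Responses: 40×1 + 40×2 + 40×2 + 30×1 + 30×1 + 30×0 = 260
- Subjects giving two responses: 40 + 40 = 80, which is 80/180 = 44% of respondents
- Planned completers among them: 35 + 35 = 70 (Protocol 11.2)

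Item 2's description of one value per subject is therefore inexact for 80 of 180 respondents. One value per product per subject is exact for all of them.

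**4. Why the descriptive table does not supply the interval.** Take equal marginal SDs s and within-subject correlation ρ. The SD of the paired difference is s√(2(1−ρ)). Table 14.2.3.3.2 gives s for each product but not ρ.

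**5. Precision available if the contrast were specified.** The SD of the paired difference is an assumption, because the documents give none. Half-width = t(0.975, 34) × SD/√35, with t = 2.032 and √35 = 5.916.

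- SD 20: 2.032 × 20/5.916 = 6.9 points
- SD 30: 2.032 × 30/5.916 = 10.3 points
- SD 40: 2.032 × 40/5.916 = 13.7 points

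**6. What a replacement model can estimate.** Five groups by two products make 10 cells. Group 1 has no VERVE rating and Groups 4 and 5 have no cigarette rating, so 7 cells are filled and 3 are empty. With a group-by-product term, main-effect least-squares means are not estimable. Contrasts between filled cells are.

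A random subject intercept cannot represent a negative correlation between the two ratings. If the true correlation were -0.3 (assumed) and the subject variance were held at zero, the standard error of the difference would be too small by a factor 1/√1.3 = 0.88, about 12%.

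**The case against.** The strongest reply is that this is a documentation gap on one open-label, subjective, secondary item, and that several tempting readings go too far. Four of them deserve an answer.

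- **A reader might infer that the one-response statement is a wrong reason for dropping the comparison.** The documents do not support that. The statement is in item 2 and explains only the loss of the maximum score. Protocol 11.7 defines that maximum for each product, and each product is rated once, so dropping it is correct for Groups 2 and 3 too. The wording is loose, but item 3 gives a different reason for the model change.
- **A reader might infer that no model or contrast was ever written.** Protocol 11.7 has both. What is missing is the modified version that Section 9 says exists.
- **A reader might infer that the trial will say nothing about VERVE against cigarettes.** Table 14.2.3.3.2 reports means with 95% intervals by product and group, so the difference in means can be read off for Groups 2 and 3. What is missing is its paired error.
- **A reader might infer that Objective 6 promises UPA results against cessation on Days 1, 5 and 7.** Its compound wording allows that. But SAP 2.4 limits UPA to Day 7, SAP 7.1.4.1 limits it to Groups 1 to 5, and SAP 7.3.3 names a cessation contrast only for QSU-Brief. The working scope is clear and only a clarifying line is needed.

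It can also be said that declaring UPA descriptive would remove the inconsistency. It would, but it would leave a contrast the protocol named unanswered with the data in hand.

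What stands is that the output list excludes the comparison, no document holds a model that can be run, and the paired contrast is not estimated.

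**Conclusion.** The point holds. The SAP, followed as written, makes no inferential UPA comparison although Objective 6 and Protocol 11.7 plan one, and its own change log refers to a model it does not contain. The size is one secondary outcome with no analysis, including 80 randomised dual users (70 planned completers) whose paired ratings yield no difference or interval. The half-widths in the working show what precision is being forgone. They rest entirely on the assumed SDs of 20 to 40 points and do not measure any bias. The primary NNAL analysis and the other biomarker analyses are untouched.

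**What to change.** In SAP 7.3.3, add these Day 7 UPA contrasts:

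- (a) Within Group 2 and within Group 3, the paired VERVE minus cigarette difference with its 95% interval, from a paired-difference analysis or an unstructured within-subject covariance, not a random intercept.
- (b) UPA for cigarettes: Group 2 versus 1 and Group 3 versus 1, with gender as a fixed effect.
- (c) UPA for VERVE: Group 2 versus 4 and Group 3 versus 5, with gender as a fixed effect.

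Report only these cell contrasts, drop the protocol's day term and geometric means, and add one comparison table.

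In SAP Section 9, state the replacement analysis under item 3 and reword item 2 to one response per product per subject. Add that UPA applies to Day 7 and Groups 1 to 5 only, and that the post-baseline cessation comparison applies to QSU-Brief only. Putting this clarification in the SAP avoids a protocol amendment.

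The cost is SAP text, one table and 2 + 2 + 2 = 6 more secondary contrasts, which SAP 7.3.3 leaves unadjusted for multiplicity along with the other subjective scores. No new data, visits or subjects are required.

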# **10. SUMMARY TABLES AND FIGURES**

Summary tables and figures are numbered following the International Conference on Harmonization (ICH) structure. Please note that all summary tables and figures will be generated using SAS® Version 9.3 or higher.

The following is a list of table numbers and titles that will be included as summary tables:

## **14.1 Demographic Data Summary Tables**

Table 14.1.1.1      Summary of Disposition by Study Group and Overall  
Table 14.1.1.2      Summary of Disposition for Screen Failures

Table 14.1.2 Demographic Summary by Study Group and Overall  
Table 14.1.3 Smoking History by Study Group and Overall

## 14.2 Data Summary Tables and Figures for Biomarkers, Product Use, and Questionnaire Responses

### 14.2.1 Urine and Blood Biomarkers Tables

#### Primary and Secondary Biomarker endpoints

##### *Total Urine NNAL*

Table 14.2.1.1.1.1 Summary of Total Urine NNAL 24-Hour Excreted (ng/24 hour) by Study Group and Study Day (mITT Population)

Table 14.2.1.1.1.2 Summary of Total Urine NNAL 24-Hour Excreted (ng/24 hour) by Study Group and Study Day (PP Population)

Table 14.2.1.1.2.1 Summary of Total Urine NNAL 24-Hour Excreted Absolute Change From Baseline (ng/24 hour) by Study Group and Study Day (mITT Population)

Table 14.2.1.1.2.2 Summary of Total Urine NNAL 24-Hour Excreted Absolute Change From Baseline (ng/24 hour) by Study Group and Study Day (PP Population)

Table 14.2.1.1.3.1 Summary of Total Urine NNAL 24-Hour Excreted Percent Change From Baseline (%) by Study Group and Study Day (mITT Population)

Table 14.2.1.1.3.2 Summary of Total Urine NNAL 24-Hour Excreted Percent Change From Baseline (%) by Study Group and Study Day (PP Population)

Table 14.2.1.1.4.1 Summary of Total Urine NNAL Adjusted for Urine Creatinine (ng/g creatinine) by Study Group and Study Day (mITT Population)

Table 14.2.1.1.4.2 Summary of Total Urine NNAL Adjusted for Urine Creatinine (ng/g creatinine) by Study Group and Study Day (PP Population)

Table 14.2.1.1.5.1 Statistical Summary of Total Urine NNAL 24-Hour Excreted (ng/24 hour) by Study Group and Study Day (mITT Population)

Table 14.2.1.1.5.2 Statistical Comparisons of Total Urine NNAL 24-Hour Excreted (ng/24 hour) Between Study Groups by Study Day (mITT Population)

Table 14.2.1.1.6.1	Statistical Summary of Total Urine NNAL 24-Hour Excreted (ng/24 hour) by Study Group and Study Day (PP Population)
Table 14.2.1.1.6.2	Statistical Comparisons of Total Urine NNAL 24-Hour Excreted (ng/24 hour) Between Study Groups by Study Day (PP Population)
Table 14.2.1.1.7.1	Statistical Summary of Total Urine NNAL 24-Hour Excreted (ng/24 hour) by Study Group (mITT Population with Imputation of Missing Data Using Last Observation Carried Forward Method) (Note: This analysis will only be performed if the percentage of missing values is greater than 5% of observations.)
Table 14.2.1.1.7.2	Statistical Comparisons of Total Urine NNAL 24-Hour Excreted (ng/24 hour) Study Groups (mITT Population with Imputation of Missing Data Using Last Observation Carried Forward Method) (Note: This analysis will only be performed if the percentage of missing values is greater than 5% of observations.)
Table 14.2.1.1.8.1	Statistical Summary of Total Urine NNAL 24-Hour Excreted (ng/24 hour) by Study Group (mITT Population with Imputation of Missing Data Using Multiple Imputation by SAS MI Procedure) (Note: This analysis will only be performed if the percentage of missing values is greater than 5% of observations.)
Table 14.2.1.1.8.2	Statistical Comparisons of Total Urine NNAL 24-Hour Excreted (ng/24 hour) Between Study Groups (mITT Population with Imputation of Missing Data Using Multiple Imputation by SAS MI Procedure) (Note: This analysis will only be performed if the percentage of missing values is greater than 5% of observations.)
Table 14.2.1.1.9.1	Summary of Total Urine NNAL 24-Hour Excreted (ng/24 hour) by Study Group and Study Day (mITT Population with Outliers Excluded)
Table 14.2.1.1.9.2	Statistical Summary of Total Urine NNAL 24-Hour Excreted (ng/24 hour) at Day 7 by Study Group (mITT Population with Outliers Excluded)
Table 14.2.1.1.9.3	Statistical Comparisons of Total Urine NNAL 24-Hour Excreted (ng/24 hour) at Day 7 Between Study Groups (mITT Population with Outliers Excluded)
Table 14.2.1.1.10.1	Statistical Summary of Total Urine NNAL 24-Hour Excreted (ng/24 hour) at Day 7 by Study Group (mITT

Population with BLQ values set to the LLOQ) (Note: This analysis will only be performed if the percentage of values that are BLQ is greater than 5% of observations.)

Table 14.2.1.1.10.2 Statistical Comparisons of Total Urine NNAL 24-Hour Excreted (ng/24 hour) at Day 7 Between Study Groups (mITT Population with BLQ values set to the LLOQ) (Note: This analysis will only be performed if the percentage of values that are BLQ is greater than 5% of observations.)

**For the following urine biomarkers, tables similar to those for Total Urine NNAL will be created as appropriate and numbered as specified:**

